# Missing date of last contact

If a patient dies and had not withdrawn consent, the date of last contact will be the date of death. If a patient did not die, the date of last contact will be the latest date of the individual trial completion date, last administration date and the last available measurement/procedure date.

## 6.7 BASELINE, TIME WINDOWS AND CALCULATED VISITS

#### 6.7.1 Baseline

The term "baseline" refers to the last available measurement prior to administration of any randomised trial medication.

The following considerations apply for laboratory measurements, if the time of the sample is missing on the day of first study medication intake:

- a) For FPG: the measurement will not be considered as baseline
- b) For all other lab investigations: The last measurement on this day will still be considered as baseline measurement.

# 6.7.2 Time windows for assignment to on-treatment phase

Measurements taken prior to the first intake of randomised trial medication will be considered pre-treatment values.

The date and clock time of the first drug administration will be used to separate pre-treatment from on-treatment values. Measurements taken after the first intake of randomised trial medication will be considered on-treatment values if they have been obtained up to end of the parameter specific follow-up period as defined in Table 6.7.2: 1 and will be assigned to the randomised trial medication for analyses.

Measurements taken after the end of the endpoint specific follow-up period will be considered post-treatment values.

## 6.8 CALCULATION OF TIME TO EVENT

This section describes the calculation of the time to event and the time that patients without an event were in the trial (under risk). See Section 6.8.3 on censoring rules.

Consistent with that approach, the respective time intervals determine the start and end for the derivation of occurrence of a specific event.

For patients with an event, the time to event is calculated as:

<date of event> - < start date> + 1

For patients without an event, the time at risk is calculated as:

<date of censoring> - < start date > + 1

TSAP for BI Trial No: 1218.22

Proprietary confidential information © 2017 Boehringer Ingelheim International GmbH or one or more of its affiliated companies

## 6.8.1 Start date

In general, the time to event will be derived from the date of randomisation, e.g. for the primary endpoint, the key secondary endpoint, their individual components, and the tertiary adjudicated endpoints.

For the endpoints of time-to-first-hypoglycemia and time-to-AE analysis,

#### **6.8.2** Date of event

For composite outcomes, e.g. time to first 3P-MACE, the earliest onset date of the corresponding components will be used

The dates determined by the adjudication committee will be used; these can be different from the investigator reported dates.

## 6.8.3 Censoring

Primary endpoints

The underlying principle is that the censoring date should be the date at which the patient was last known to be free of an endpoint event (e.g. free of each component of the 3P-MACE).

Patients without occurrence of a specific endpoint (composite endpoint or individual components) will be considered censored at the individual day of trial completion\*.

- \* This is defined as the latest of the following dates as of
  - adverse event/outcome event start dates (if non-fatal event),
  - onset dates of adjudicated (by adjudication confirmed and non-confirmed) events (if non-fatal event),
  - date of trial completion (defined as latest of date of last clinic visit, last telephone contact, date of last contact if lost to follow-up).

For patients who died during the study, the date until which follow-up for non-fatal outcome events was performed will be used for censoring.

Censoring is considered independent from trial drug intake.

Generally, the 7 days censoring definition will be used for adverse events incl. hypoglycaemia.

All of the above mentioned x-day censoring rules will be handled as follows:

Patients who did not experience the event will be censored at the earliest date between the individual day of trial completion (defined above) and x days after last intake of study drug. For this analysis events will be considered that occurred not later than x days after last intake of study drug, or until individual day of trial completion (defined above), whichever is earlier.

Endpoints based only on laboratory data (by adjudication confirmed or not)

Patients who already fulfil the respective condition at baseline are generally not considered in the number of patients at risk for this endpoint (

If a baseline laboratory measurement is not available for the parameter of interest, it is assumed that the patient did not experience the condition corresponding to the endpoint at baseline and the patient is included in the patients at risk for this endpoint.

Patients without an event and available post-baseline laboratory measurements will be considered censored at the date of last laboratory sampling of the corresponding parameter. Patients with missing baseline laboratory required to derive a change from baseline and patients without laboratory data following the baseline measurement will be censored on the day of randomisation or date of first study drug intake, respectively.

Page 51 of 80

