**Early discontinuation of study medication is not a criterion for withdrawal of consent for participating in the study.**

If a patient becomes pregnant during the trial, the study treatment will be stopped, the patient will be followed up during the study and until birth or termination of the pregnancy (see further details in [Section 5.2.2.2](#)).

If pancreatitis is suspected, the study treatment should be stopped.

**An individual patient is to be withdrawn from the study and follow up assessments only if the patient actively withdraws consent, without the need to justify the decision.**

Proprietary confidential information.

© 2016 Boehringer Ingelheim International GmbH or one or more of its affiliated companies. All rights reserved.

This document may not - in full or in part - be passed on, reproduced, published or otherwise used without prior written permission.

A patient has the right to withdraw informed consent for participation at any time for any reason. However, withdrawal of consent from study participation should be very rare and unusual. Because of this, the investigator should be involved in the discussions with the patient regarding a withdrawal of consent. Additionally, the investigator should discuss the withdrawal of consent with the sponsor representative prior to stopping study participation.

Patients that are not actively taking study drug may be less motivated to adhere to the study visit schedule. Investigators and site staff should work to detect early signs of losing interest and readily present such patients (not actively taking study drug) with the following options to encourage continued participation:

- Option 1 Continue to attend regularly scheduled study visits at the site until the study ends
- Option 2 Conduct all remaining study visits over the phone
- Option 3 Discontinue participation in remaining study activities but permit collection of vital status and CV outcome events at minimum at the end of the study through the patient or alternative person designated by the patient (e.g., family, spouse, partner, legal representative, or physician) even if only by telephone
- Option 4 Discontinue participation in remaining study activities but permit collection of vital status at minimum at the end of the trial through the patient, alternative person designated by the patient, or through review of patient's medical information from alternative sources (e.g., doctor's notes, hospital records, etc.)

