Patients will be asked to choose the most rigorous form of follow-up that they are willing to comply with.

Patients who refuse all four of the above are considered to have fully withdrawn informed consent to participate in the study. A patient should be withdrawn from the study and all follow up assessments only if the patient refused all four options and withdraws informed consent, without the need to justify the decision. Where allowed, patients should be followed-up for vital status.

If the patient withdraws informed consent for participation in the study, the study will end for that patient. The patient should stop taking study medication and should be asked to complete the EOT and follow-up procedures as described in the [Flow Chart](#). Completing these procedures is strongly recommended for the patient's safety. A patient could be instructed to stop the study treatment only after discussion between sponsor representative and investigator, if eligibility criteria are being violated, or if the patient fails to comply with the protocol (e.g. non-attendance at study assessments). Patients that withdraw informed consent or discontinue from the study after randomization will not be replaced.

If a patient is lost, every effort should be made by the Investigator and site staff to contact and locate the patient before the patient is declared lost to follow-up. Investigators and site staff should use every possible allowable means to locate patients

Proprietary confidential information.

© 2016 Boehringer Ingelheim International GmbH or one or more of its affiliated companies. All rights reserved.

This document may not - in full or in part - be passed on, reproduced, published or otherwise used without prior written permission.

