# 6.8.4 Definition of lost-to follow-up for vital status

If a patient could not be followed up at study termination for primary endpoint information or respectively vital status could not be collected, this patient will be considered as Lost-To-Follow-Up (LTFU) for 3P-MACE or respectively as LTFU for vital status. Study termination is defined by the start of the close-out period. The number of patients and frequency will be provided.

Patients with an adjudicated event for the primary endpoint event are not regarded as LTFU for 3P-MACE. Patients who died are not regarded as LTFU for vital status.

The close-out period is defined as the time period communicated to the site to schedule the end of trial visit (EOT).

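### Does SAP 6.8.3 let a contact that yields only vital status set the 3P-MACE censoring date of a living patient?

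*SAP*

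**What the plan says.** SAP 6.8.3 begins with a principle: "the censoring date should be the date at which the patient was last known to be free of an endpoint event", explained there as free of each component of 3P-MACE. It then gives a working date for patients without an event, the individual day of trial completion. This is the latest of three things: start dates of non-fatal adverse or outcome events, onset dates of non-fatal adjudicated events, and the "date of trial completion (defined as latest of date of last clinic visit, last telephone contact, date of last contact if lost to follow-up". Patients who died have their own rule: "For patients who died during the study, the date until which follow-up for non-fatal outcome events was performed will be used for censoring".

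SAP 6.8.4 separates two kinds of loss. If endpoint information, or vital status, could not be collected at study termination, "this patient will be considered as Lost-To-Follow-Up (LTFU) for 3P-MACE or respectively as LTFU for vital status". It adds: "The number of patients and frequency will be provided".

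Protocol 3.3.4.1 offers four levels of continued participation to patients who are off study drug. Option 3 is to "permit collection of vital status and CV outcome events at minimum at the end of the study". Option 4 is weaker: "Discontinue participation in remaining study activities but permit collection of vital status at minimum at the end of the trial". For patients who refuse all four the protocol says: "Where allowed, patients should be followed-up for vital status". Protocol 7.1 counts an adjudicated CV death even when it falls after the censoring date.

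**The concern.** The working date asks when the patient was last contacted, not what was learned then. Suppose an Option 4 patient is telephoned at study end and only survival is established. Read literally, the list treats that call as the last telephone contact, and the patient stays in the risk set for MI and stroke up to that date. SAP 6.8.4 would class the same patient as lost for 3P-MACE. The SAP makes the distinction there, and again for patients who died, but not in the visible rule for survivors.

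Over that stretch only CV death can be counted, so event rates and Kaplan-Meier estimates are diluted. If the arms differ in how much such time they hold, the hazard ratio moves as well. In a non-inferiority safety trial the awkward case is more unassessed time on linagliptin, because that pulls the estimate down, towards meeting the 1.3 margin.

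**Working it through.** **Who can be affected**

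- Clinic visits collect outcome events. The minimum yearly and study-end telephone calls in Protocol 3.1 and 3.3.4.1 are required in order to document outcome events as well as vital status. Option 2 carries out the study visits by telephone, and Option 3 collects CV outcomes.
- Option 4 sets vital status as a minimum. It does not mention telephone, and it allows review of doctor's notes and hospital records, which may also reveal an MI or stroke.
- For fully withdrawn patients Protocol 3.3.4.1 says the study ends. A later check that the patient is alive is not clearly any of the contacts listed in 6.8.3, so this route is not supported.

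What remains is an Option 4 patient whose survival-only information is recorded as a telephone or last contact.

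**The plan's own figure**

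Inputs from Protocol 7.6: margin 1.3, one-sided alpha 2.5%, power 90%, true HR 1, allocation 1:1.

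Events = 4 × (1.960 + 1.282)² / (ln 1.3)² = 610.6, so 611, as stated.

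With 611 events the upper 95% limit is HR × exp(1.96 × 2/√611) = HR × 1.172. Non-inferiority is shown at an observed HR up to 1.3/1.172 = 1.109.

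**Effect on the hazard ratio**

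Let u be the share of person-time with vital status only (uL on linagliptin, uP on placebo) and c the share of events that are CV deaths. The documents give neither, so both are assumed, with c from 0.3 to 0.5. No MI or stroke is taken to be captured in the unassessed time, which is the worst case. True HR is 1.00.

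- Current rule: HR = [1 − uL(1 − c)] / [1 − uP(1 − c)].
- Alternative, censoring survivors at the last MI/stroke assessment while later CV deaths still count: HR = [1 + c·uL/(1 − uL)] / [1 + c·uP/(1 − uP)].

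Example with uL = 1%, uP = 3%, c = 0.3. Current: 0.993/0.979 = 1.014. Alternative: 1.0030/1.0093 = 0.994.

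| uL vs uP | Current rule: HR (upper limit), c = 0.3; 0.5 | Alternative: HR (upper limit), c = 0.3; 0.5 |
|---|---|---|
| equal | 1.000 (1.172) | 1.000 (1.172) |
| 1% vs 2% | 1.007; 1.005 (1.180; 1.178) | 0.997; 0.995 (1.168; 1.166) |
| 1% vs 3% | 1.014; 1.010 (1.189; 1.184) | 0.994; 0.990 (1.165; 1.160) |
| 3% vs 1% | 0.986; 0.990 (1.155; 1.160) | 1.006; 1.010 (1.179; 1.184) |

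A Cox simulation agrees to within 0.001. It used 2 million patients per arm, a hazard of 0.0356 per year taken from the original 4-point planning rate, entry over 36 months and 54 months in total.

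**Effect on rates**

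With equal shares of 1% or 3%, rates read u(1 − c) too low under the current rule: 0.5–0.7% or 1.5–2.1%. Under the alternative they read c·u/(1 − u) too high: 0.3–0.5% or 0.9–1.5%.

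**Tipping point**

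With uL = 0, the upper limit reaches 1.3 when uP = (1 − 1.172/1.3)/(1 − c). That is 14.1% at c = 0.3 and 19.7% at c = 0.5.

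**Scale in events**

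If 1% of 7000 patients had a one-year gap, that is 70 patient-years. At 0.0356 per year about 2.5 first events would be expected in it, or 0.4% of 611. This is an upper bound, because CV deaths are still captured.

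**The case for a change.** The best argument for acting is that programmers code the definition and not the sentence above it. The distinction already exists in 6.8.4 and in the rule for deaths, so carrying it over to survivors would take one sentence. If the principle governs anyway, writing it out changes no intended analysis. SAP 6.8.4 reports only how many patients are lost, so a reader could not see unassessed time by arm. FDA acceptance of the revised SAP does not by itself settle a difference between two of its sections.

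The wording gap stands: no visible text ties a living patient's last contact to endpoint assessment. The case for a new primary rule does not. Protocol 7.1 keeps counting CV deaths after the last assessment, so dropping the survivors' matching time inflates the rate in whichever arm has more such time. When CV death is half of events this error is as large as the present one. Below half it is smaller, but the documents do not give the share. With more unassessed time on placebo, the alternative would favour linagliptin. Nor does any visible passage show that MI/stroke status is recorded contact by contact for survivors.

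The visible rule may also be incomplete. Section 6.8.3 refers back to several x-day censoring rules while only a 7-day rule can be seen, so a qualifier may sit in text that is not available.

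**Conclusion.** This is a gap in wording that the section's own principle already fills. An analyst who has read the first sentence of 6.8.3 has no reason to treat a survival-only call as proof of freedom from MI and stroke, and 6.8.4 makes the patients concerned identifiable. If the list were applied literally, equal gaps would leave the hazard ratio at 1.00. An assumed 1% against 3% would shift it by 0.010 to 0.014 in either direction, with the upper limit no higher than 1.189. The alternative rule would replace that with a shift of 0.006 to 0.010 the other way. The non-inferiority conclusion is not at risk short of roughly 14% to 20% unassessed time in one arm and none in the other.

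The TS+30 analysis in Protocol 7.3.1 censors 30 days after permanent discontinuation. It therefore removes most of this time, since Option 4 is meant for patients who are off drug.

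These sizes rest on assumed shares of unassessed time, an assumed CV-death share of 30% to 50%, a roughly constant hazard, and no MI or stroke captured during the gap. The sponsor can be asked to confirm that the principle governs vital-status-only contacts, but the primary censoring rule should stay as it is.

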# 6.8.4 Definition of lost-to follow-up for vital status

If a patient could not be followed up at study termination for primary endpoint information or respectively vital status could not be collected, this patient will be considered as Lost-To-Follow-Up (LTFU) for 3P-MACE or respectively as LTFU for vital status. Study termination is defined by the start of the close-out period. The number of patients and frequency will be provided.

Patients with an adjudicated event for the primary endpoint event are not regarded as LTFU for 3P-MACE. Patients who died are not regarded as LTFU for vital status.

The close-out period is defined as the time period communicated to the site to schedule the end of trial visit (EOT).

# 7. PLANNED ANALYSIS

For End-of-text and appendix tables, the set of summary statistics is: N / Mean / standard deviation (SD) / Min / Q1 (lower quartile) / Median / Q3 (upper quartile) / Max.

Baseline data will be presented overall and per treatment group.

The 1st and 99th percentiles might be substituted for minimum and maximum in tables with open-ended values to safeguard against implausible extremes.

Geometric means and ranges can be added to the presentation or replace the presentation of mean and standard deviation for parameters which rather follow a log-normal distribution than a normal distribution.

Tabulations of frequencies for categorical data will include all possible categories and will display the number of observations in a category as well as the percentage (%) relative to the respective treatment group. The category missing will be displayed only if there are actually missing values. In general, unless otherwise specified, percentages will be based on all patients in the respective patient set, irrespective of whether they have missing values or not.

Statistical parameters will be displayed to a defined number of decimal places as specified in the Global Biostatistics Standard Output Conventions (1), with exception of p-values presentation which will be displayed with 4 decimal places.

A general overview on patient disposition will be provided by treatment group and in total and presented in the clinical trial report by frequency tabulations. This will include the number of patients screened, randomised, screened but not randomised, treated as well as those who did/ did not prematurely discontinue trial medication, did/did not prematurely discontinue from trial by region/country/centre. See also Table 9.1: 1 Table 9.1: 1 for assignment of countries to region. The reason for not randomising screened patients will also be summarized.

In addition, the number of patients who discontinued trial medication due to fatal and non-fatal adverse events will be displayed for public data disclosure on European Union Drug Regulating Authorities Clinical Trials (EudraCT). Additionally, baseline data analyses of screened patients by country and by age groups will be done for EudraCT.

The frequency of patients with important protocol violations as well as the frequency of patients in the different analysis sets will be presented by randomised treatment group.

The number of patients included in each analysis set will be displayed with percentages based on the randomised set.

#### 7.4 PRIMARY ENDPOINT

# 7.4.1 Primary analysis

The primary analysis on the primary endpoint time to first 3P-MACE (cf. Section 5.1) will be performed on the TS.

**Section 7.1 of the CTP**: For the primary objective the upper bound of the two-sided (1-2\*alpha) confidence interval which equals the upper bound of the one-sided (1-alpha) confidence interval will be used to investigate non-inferiority (NI) of linagliptin versus placebo regarding the hazard ratio (HR) of the primary endpoint. The non-inferiority margin is chosen as 1.3. The overall one-sided significance level is 2.5%.

The allocated trial treatment at randomisation will be used for analysis, and all events which occur until trial end will be taken into account.

The time to the primary endpoint will be derived from the date of randomisation. The censoring rules are described in Section 6.8.3.

Hypotheses tested are described in the Section 7.2 of the CTP.

#### Statistical methods

For the primary analysis, a Cox proportional hazard regression model will be performed to compare the effect of linagliptin versus placebo. The model will include randomised treatment and geographical region as factors. Breslow's method will be used for dealing with ties. The SAS PHREG procedure will be used.

The hypothesis of non-inferiority will be tested at the one-sided significance level of  $\alpha_1$ =2.5%.

The hazard function of an event for patient j at time t is assumed to have the form:

$$h_i(t) = \exp(\beta_1 x 1_i + \beta_2 x 2_i) h_0(t), j=1,...,n,$$

where

- $\circ$  h0(t) is the non-negative baseline hazard function for a patient with a value of zero for the explanatory value  $x1_i$  and  $x2_i$
- o β1 is the (unknown) coefficient of the explanatory variable x1
- $\circ$  x1j is an indicator variable representing the treatment group for patient j=1,...,n

- o β2 is the (unknown) coefficient of the explanatory variable x2
- o x2j is an indicator variable representing the geographical region for patient j=1,...,n

The hazard ratio (HR) for the effect of treatment (linagliptin vs. placebo), adjusted for geographical region, will be presented with the 95% confidence interval, the 99% confidence interval and the p-values based on the Wald Chi-Square statistic: one-sided p-value for the non-inferiority test (NI margin 1.3), the one-sided p-value for the superiority test and the two-sided p-value.

Non-inferiority of the primary endpoint will be investigated by comparing the upper limit of the two sided 95% confidence interval of the hazard ratio with the non-inferiority margin of 1.3: if the upper limit is less than 1.3, non-inferiority has been demonstrated.

In case non-inferiority of the primary endpoint is demonstrated, then superiority of the primary endpoint and superiority of the key secondary endpoint will be investigated:

For the final analysis, the first hypothesis (non-inferiority of the primary endpoint) will be tested at the one-sided alpha-level of 2.5%. In case of significance, the null hypothesis is rejected in a confirmatory sense and the next set of hypotheses (two separate hypothesis tests) will be tested: a) test of the primary endpoint for superiority and b) test of the composite renal endpoint for superiority.

To adjust for multiplicity a sequentially rejective multiple test procedure will be applied (3). Both one-sided hypotheses H0(Sup1) and H0(Sup2) will be tested separately, at the initial alpha-levels of 0.2\*alpha for 3-point MACE and 0.8\*alpha for the composite renal endpoint, respectively. If both null hypotheses cannot be rejected at these initial alpha-levels, the procedure stops and for none of these endpoints superiority can be declared. After having shown superiority for one of these endpoints, the used alpha can be shuffled to the other test: If H0(Sup2) is rejected at the alpha-level of 0.8\*alpha, then H0(Sup1) can be tested at the full alpha-level of 2.5% (one-sided). If H0(Sup1) is rejected at the alpha-level of 0.2\*alpha, then H0(Sup2) can be tested at the full alpha-level of 2.5% (one-sided).

